11.9.8. Efficacy Figures

Efficacy: Figures						
No.	Population	IDSL / Example Shell	Title	Programming Notes	Deliverable	
					If study stops	If study continues
2.1	Micro-ITT NTF-S	EFF_F1	Percent of Therapeutic Success by Visit, Overall and by Qualifying Uropathogen Isolated at Baseline	by uropathogen	AAC	AAC
2.2	Micro-ITT		Forest Plot for Therapeutic Success Rate Overall and by Subgroup		AAC	AAC
2.3	Micro-ITT NTF-S		Forest Plot for Therapeutic Success Rate Overall and by Subgroup	If the studies stop early for efficacy, please include a row on the micro-ITT NTF-S (IA Set) as this will be the primary analysis	AAC	AAC
2.4	Micro-ITT NTF-NS		Forest Plot for Therapeutic Success Rate Overall and by Subgroup		AAC	AAC
2.5	Micro-ITT/NTF-S/NTF-NS		Forest Plot for Therapeutic Success Rate by Qualifying Baseline Uropathogen and Uropathogen Phenotypic and Genotypic Subcategories	by population (Micro-ITT, Micro-ITT-NTF-S, Micro-ITT NTF-NS) and visit (TOC/FU)	AAC	AAC
2.6	Micro-ITT/NTF-S/NTF-NS		Forest Plot for Clinical Success Rate by Qualifying Baseline Uropathogen and Uropathogen Phenotypic and Genotypic Subcategories	by population (Micro-ITT, Micro-ITT-NTF-S, Micro-ITT NTF-NS) and visit (TOC/FU)	AAC	AAC
2.7	Micro-ITT/NTF-S/NTF-NS		Forest Plot for Microbiological Success Rate by Qualifying Baseline Uropathogen and Uropathogen Phenotypic and Genotypic Subcategories	by population (Micro-ITT, Micro-ITT-NTF-S, Micro-ITT NTF-NS) and visit (TOC/FU)	AAC	AAC
2.8	Micro-ITT NTF-S or		Tipping Point Analysis of Therapeutic Response at TOC	This will be produced for the primary analysis set (i.e. the	SAC	SAC

Efficacy: Figures						
No.	Population	IDSL / Example Shell	Title	Programming Notes	Deliverable	
					If study stops	If study continues
	Micro-ITT NTF-S (IA Set) (see notes)			IA Set if the study is stopped early for efficacy)		
2.11	Intent-to-Treat	EFF_F3	Boxplot of Individual Clinical Symptom Score and Total Score by Visit		AAC	AAC
2.1101	Intent-to-Treat	EFF_F3	Boxplot of Change from Baseline Individual Clinical Symptom Score and Total Score by Visit		AAC	AAC
2.12	Intent-to-Treat	EFF_F1	Percent of Clinical Outcome by Visit		AAC	AAC
2.1301	Micro-ITT	EFF_F1	Percent of Microbiological Outcome by Visit, Overall and by Qualifying Uropathogen Isolated at Baseline	by visit (TOC/FU)	AAC	AAC
2.1302	Micro-ITT NTF-S	EFF_F1	Percent of Microbiological Outcome by Visit, Overall and by Qualifying Uropathogen Isolated at Baseline	by visit (TOC/FU)	AAC	AAC
2.1303	Micro-ITT NTF-NS	EFF_F1	Percent of Microbiological Outcome by Visit, Overall and by Qualifying Uropathogen Isolated at Baseline	by visit (TOC/FU)	AAC	AAC

CCI

11.9.9. Safety Tables

Safety: Tables						
No.	Population	IDSL / Example Shell	Title	Programming Notes	Deliverable	
					If study stops	If study continues
Adverse Events (AEs)						
3.0	Safety		Overall Summary of Adverse Events		HDL	HDL
3.1	Safety	AE5B	Summary of Adverse Events by System Organ Class and Preferred Term and Maximum Grade		HDL	HDL
3.2	Safety	AE5B	Summary of Adverse Events by System Organ Class and Preferred Term and Maximum Grade and Age	subgroup age group	SAC	SAC
3.3	Safety	AE5B	Summary of Drug-Related Adverse Events by System Organ Class and Preferred Term and Maximum Grade		SAC	SAC
3.4	Safety	AE3	Summary of Common ($\geq 1\%$) Adverse Events by Preferred Term		SAC	SAC
3.5	Safety	AE3	Summary of Common ($\geq 1\%$) Adverse Events by Preferred Term and Age	subgroup age group	SAC	SAC
3.6	Safety	AE15	Summary of Common ($\geq 1\%$) Non-Serious Adverse Events by System Organ Class and Preferred Term (Number of Participants and Occurrences)		SAC	SAC
3.7	Safety	AE3	Summary of Common ($\geq 1\%$) Grade 2-5 Adverse Events by Preferred Term		SAC	SAC

Safety: Tables						
No.	Population	IDSL / Example Shell	Title	Programming Notes	Deliverable	
					If study stops	If study continues
3.9	Safety	E16	Summary of Serious Adverse Events by System Organ Class and Preferred Term (Number of Subjects and Occurrences)		SAC	SAC
3.10	Safety	AE5B	Summary of Serious Adverse Events by System Organ Class and Preferred Term and Maximum Grade		SAC	SAC
3.11	Safety	AE5B	Summary of Serious Adverse Events by System Organ Class and Preferred Term and Maximum Grade and Age	subgroup age group	SAC	SAC
3.12	Safety	AE5B	Summary of Drug-Related Serious Adverse Events by System Organ Class and Preferred Term and Maximum Grade		SAC	SAC
3.13	Safety	AE3	Summary of Non-Fatal Serious Adverse Events		SAC	SAC
3.14	Safety	AE3	Summary of Drug-Related Non-Fatal Serious Adverse Events		SAC	SAC
3.15	Safety	AE5B	Summary of Cardiovascular and Gastrointestinal Adverse Events of Special Interest by System Organ Class and Preferred Term and Maximum Grade		SAC	SAC
3.17	Safety	AE5B	Summary of Acetylcholinesterase-Inhibition Adverse Events of Special Interest by System Organ Class and Preferred Term and Maximum Grade		SAC	SAC

Safety: Tables						
No.	Population	IDSL / Example Shell	Title	Programming Notes	Deliverable	
					If study stops	If study continues
3.19	Safety	AE5B	Summary of Acetylcholinesterase-Inhibition Adverse Events of Special Interest by Number of Events and Unique Preferred Term	a Table to summarize the number and % of patients experiencing 1, 2, 3, 4, 5 or more events and 1,2,3,4,>=5 or more distinct PTs.	SAC	SAC
3.20	Safety	AE5B	Summary of Acetylcholinesterase-Inhibition Adverse Events of Special Interest by Number of Events and Unique Preferred Term and Age	subgroup age group	SAC	SAC
3.21	Safety		Summary of Onset, Duration and Lag Time of AChE-I Event	a summary Table to present the statistics (mean, median, max, min) of time to first event, duration, and lag time since last dose for AchEI, non-GI AchEI, and GI AchEI events	SAC	SAC
3.22	Safety		Summary of Onset, Duration and Lag Time of AChE-I Event by Age	subgroup age group	SAC	SAC
3.23	Safety	AE5B	Summary of Adverse Events Leading to Discontinuation of Study Treatment or Withdrawal from Study by System Organ Class and Preferred Term and Maximum Grade		SAC	SAC
3.2301	Safety	AE5B	Summary of Adverse Events Leading to Discontinuation of Study Treatment by System Organ Class and Preferred Term and Maximum Grade		SAC	SAC

Safety: Tables						
No.	Population	IDSL / Example Shell	Title	Programming Notes	Deliverable	
					If study stops	If study continues
Laboratory						
3.24	Safety	LB1	Summary of Clinical Chemistry Values Change from Baseline		SAC	SAC
3.25	Safety	LB2	Summary of Emergent Chemistry Laboratory Results by Maximum Grade Increase from Baseline		SAC	SAC
3.26	Safety	LB1	Summary of Hematology Change from Baseline		SAC	SAC
3.27	Safety	LB2	Summary of Emergent Hematology Laboratory Results by Maximum Grade Increase from Baseline		SAC	SAC
3.28	Safety	LIVER1	Summary of Liver Monitoring/Stopping Event Reporting		SAC	SAC
3.29	Safety	UR3	Summary of Urinalysis Results		SAC	SAC
3.30	Safety	LIVER10	Summary of Hepatobiliary Laboratory Abnormalities		SAC	SAC

Safety: Tables						
No.	Population	IDSL / Example Shell	Title	Programming Notes	Deliverable	
					If study stops	If study continues
Vital Signs						
3.31	Safety	VS3	Summary of Worst-Case Vital Signs Results Relative to Potential Clinical Importance Criteria Post-Baseline Relative to Baseline		SAC	SAC
3.32	Safety	VS1	Summary of Change from Baseline in Vital Signs		SAC	SAC
3.33	Safety		Summary of Maximum Actual and Change from Baseline for Electrocardiogram Parameter Corrected QTc Interval		SAC	SAC
Family History						
3.34	Safety	FH1	Summary of Family History of Cardiovascular Risk Factors		SAC	SAC

11.9.10. Safety Figures

Safety: Figures						
No.	Population	IDSL / Example Shell	Title	Programming Notes	Deliverable	
					If study stops	If study continues
3.1	Safety	AE10	Plot of Common ($\geq 1\%$) Adverse Events and Relative Risk		AAC	AAC
3.2	Safety	AE11	Cumulative Distribution of Time to First Gastrointestinal Event		AAC	AAC
3.3	Safety		Stacked Bar Chart of AChE-I Cumulative Grades		AAC	AAC
3.4	Safety		Stacked Bar Chart of non-GI AChE-I Cumulative Grade		AAC	AAC
3.5	Safety		Bar Chart of GI Events by Grade in Percentage of Subjects over Time		AAC	AAC
3.6	Safety		Plot for AChE-I Events and Relative Risk		AAC	AAC
3.7	Safety		Plot of Maximum Post-Baseline vs Baseline for ALT		AAC	AAC
3.8	Safety		Plot of Maximum Post-Baseline Total Bilirubin vs Maximum Post-Baseline ALT		AAC	AAC
3.9	Safety		Liver Function Tests Patient Profiles		AAC	AAC

11.9.11. ICH and Non-ICH Listings

Listings						
No.	Population	IDSL / Example Shell	Title	Programming Notes	Deliverable	
					If study stops	If study continues
Participant Disposition						
1	Intent-to-Treat	ES2	Listing of Reasons for Study Withdrawal	ICH Listing	AAC	AAC
2	Intent-to-Treat	SD2	Listing of Reasons for Study Treatment Discontinuation	ICH Listing	AAC	AAC
3	Intent-to-Treat	SP3	Listing of Subjects Excluded from Any Population	ICH Listing	AAC	AAC
Protocol Deviations						
4	Intent-to-Treat	DV2	Listing of Important Protocol Deviations	ICH Listing	AAC	AAC
5	Screened	ES7	Listing of Reasons for Screen Failure	Non-ICH Listing	AAC	AAC
6	Intent-to-Treat	BL1	Listing of Subjects for Whom the Treatment Blind was Broken During the Study	ICH Listing	AAC	AAC
7	Intent-to-Treat	TA1	Listing of Randomized and Actual Treatments	Non-ICH Listing	pre-HDL (2 days post unblinding)	pre-HDL (2 days post unblinding)
8	Intent-to-Treat	IE3	Listing of Subjects with Inclusion/Exclusion Criteria Deviations	ICH Listing	AAC	AAC
Demographic and Baseline Characteristics						
9	Intent-to-Treat	DM2	Listing of Demographic Characteristics	ICH Listing	AAC	AAC
10	Intent-to-Treat	DM9	Listing of Race	ICH Listing	AAC	AAC
11	Intent-to-Treat	SAFE_L1	Listing of History of Uncomplicated Urinary Tract Infection and Pre-Existing Conditions with Similar Symptoms	ICH Listing	AAC	AAC

Listings						
No.	Population	IDSL / Example Shell	Title	Programming Notes	Deliverable	
					If study stops	If study continues
12	Intent-to-Treat	MH2	Listing of Medical Conditions	ICH Listing	AAC	AAC
12.1	Intent-to-Treat	MH2	Listing of Findings of Medical History	ICH Listing	AAC	AAC

Listings						
No.	Population	IDSL / Example Shell	Title	Programming Notes	Deliverable	
					If study stops	If study continues
Prior and Concomitant Medications						
13	Intent-to-Treat	CM3	Listing of Prior and Concomitant Medications	Non-ICH Listing	AAC	AAC
14	Intent-to-Treat	CM3	Listing of Prior and Concomitant Antibiotic Medications for uUTI	Non-ICH Listing	AAC	AAC
Exposure and Treatment Compliance						
15	Intent-to-Treat	EX3	Listing of Exposure Data	ICH Listing	AAC	AAC
Efficacy						
16	Micro-ITT		Listing of Microbiological Outcome and Response, Clinical Outcome and Response, and Therapeutic Response by Subject ID and Baseline Qualifying Uropathogen	Non-ICH Listing	AAC	AAC
17	Intent-to-Treat	EFF_L1	Listing of Clinical Outcome and Response	Non-ICH Listing	AAC	AAC
CCI						
20	Intent-to-treat	EFF_L3	Listing of Susceptibility Results	Non-ICH Listing	AAC	AAC
21	Micro-ITT	EFF_L4	Listing of Clinical Response, Microbiological Outcome and Response, Therapeutic Response, Study Drug MIC and Zone Diameter Results by Qualifying Baseline Uropathogen	Non-ICH Listing	AAC	AAC

Listings						
No.	Population	IDSL / Example Shell	Title	Programming Notes	Deliverable	
					If study stops	If study continues
22	Intent-to-Treat	EFF_L4	Listing of Clinical Response, Microbiological Outcome and Response, Therapeutic Response, MIC and Zone Diameter Results for Uropathogens with a 4-fold Increase in Study Treatment MIC	Non-ICH Listing	AAC	AAC
CCI						
24	Intent-to-treat		Listing of Genetic Characterization Results	Non-ICH Listing	AAC	AAC
25	Intent-to-treat		Listing of New Qualifying Uropathogens	Non-ICH Listing	AAC	AAC
26	Micro-ITT		Listing of Sequence Typing and Phenotypic Subcategories for Qualifying Uropathogens from Microbiological Failures	Non-ICH Listing	AAC	AAC
Adverse Events						
27	Safety	AE2	Listing of Relationship Between System Organ Class and Verbatim Text	Non-ICH Listing	AAC	AAC
28	Safety	AE7	Listing of Subject Numbers for Individual Adverse Events	ICH Listing	AAC	AAC
29	Safety	AE8CP	Listing of All Adverse Events	ICH Listing	AAC	AAC
Serious and Other Significant Adverse Events						
30	Safety	AE8CP	Listing of Study Drug Related Adverse Events	ICH Listing	AAC	AAC
31	Safety	SAFE_L2	Listing of Serious Adverse Events (Fatal & Non-Fatal)	ICH Listing	HDL	HDL
31.1	Safety		Listing of Fatal Serious Adverse Events	ICH Listing	AAC	AAC
32	Safety	AE8CP	Listing of Adverse Events Leading to Discontinuation of Study Treatment or Withdrawal from Study	ICH Listing	AAC	AAC

Listings						
No.	Population	IDSL / Example Shell	Title	Programming Notes	Deliverable	
					If study stops	If study continues
33	Safety	AE8CP	Listing of Cardiovascular and Gastrointestinal Adverse Events of Special Interest	ICH Listing	AAC	AAC
34	Safety	AE8CP	Listing of Acetylcholinesterase-Inhibition Adverse Events of Special Interest	ICH Listing	AAC	AAC
35	Safety	AE8CP	Listing of Non-Gastrointestinal Acetylcholinesterase-Inhibition Adverse Events of Special Interest	ICH Listing	AAC	AAC
All Laboratory						
36	Safety	LB5A	Listing of Clinical Chemistry Toxicities of Grade 3 or Higher	ICH Listing	AAC	AAC
37	Safety	LB5A	Listing of All Clinical Chemistry Data for Subjects with Toxicities of Grade 3 or Higher	ICH Listing	AAC	AAC
38	Safety	LB5A	Listing of Hematology Toxicities of Grade 3 or Higher	ICH Listing	AAC	AAC
39	Safety	LB5A	Listing of Hematology Data for Subjects with Toxicities of Grade 3 or Higher	ICH Listing	AAC	AAC
40	Safety	UR2A	Listing of Urinalysis Data	ICH Listing	AAC	AAC
ECG						
41	Safety	EG5	Listing of All ECG Findings for Subjects with an Abnormal Finding	Non-ICH Listing	AAC	AAC
42	Safety	EG3	Listing of All ECG Values for Subjects with Any Value of Potential Clinical Importance	Non-ICH Listing	SAC	SAC

Listings						
No.	Population	IDSL / Example Shell	Title	Programming Notes	Deliverable	
					If study stops	If study continues
Vital Signs						
43	Safety	VS4	Listing of All Vital Signs for Subjects with Potential Clinical Importance Values	Non-ICH Listing	AAC	AAC
Liver Events and Other Safety Endpoints						
44	Safety	SAFE_L3	Listing of Clostridium Difficile Testing Results	Non-ICH Listing	AAC	AAC
45	Safety	SU2	Listing of Alcohol Intake at Onset of Liver Event	Non-ICH Listing	AAC	AAC
46	Safety	LIVER5	Listing of Liver Monitoring/Stopping Event Reporting	Non-ICH Listing	AAC	AAC
47	Safety	LIVER7	Listing of Liver Biopsy Details	Non-ICH Listing	AAC	AAC
48	Safety	LIVER8	Listing of Liver Imaging Details	Non-ICH Listing	AAC	AAC
COVID-19						
51	Intent-to-Treat		Listing of Substance Use	Non-ICH Listing	AAC	AAC
52	Intent-to-Treat	PAN5A	Country Level Listing of Start Dates of Waves of COVID-19 Pandemic Measures	Non-ICH Listing	AAC	AAC
53	Intent-to-Treat	PAN7	Listing of All Subjects with Visits and Assessments Impacted by COVID-19 Pandemic	Non-ICH Listing	AAC	AAC
54	Safety	PAN12	Listing of COVID-19 Assessments and Symptom Assessments for Subjects with COVID-19 Adverse Events	Non-ICH Listing	AAC	AAC
55	Intent-to-Treat	PREG1	Listing of Subjects Who Became Pregnant During the Study	Non-ICH Listing	AAC	AAC

[figure not shown]
Listings						
No.	Population	IDSL / Example Shell	Title	Programming Notes	Deliverable	
					If study stops	If study continues
56	Intent-to-Treat	LIVER15	Liver Stopping Event Profile	Non-ICH Listing Conditional output that will only be produced if participant have corresponding event	AAC	AAC
57	Intent-to-Treat	ARR1	Patient Profile for Arrhythmias	Non-ICH Listing Conditional output that will only be produced if participant have corresponding event	AAC	AAC
58	Intent-to-Treat	CHF1	Patient Profile for Congestive Heart Failure	Non-ICH Listing Conditional output that will only be produced if participant have corresponding event	AAC	AAC
59	Intent-to-Treat	CVATIA1	Patient Profile for Cerebrovascular Events, Stroke and Transient Ischemic Attack	Non-ICH Listing Conditional output that will only be produced if participant have corresponding event	AAC	AAC

[figure not shown]
Listings						
No.	Population	IDSL / Example Shell	Title	Programming Notes	Deliverable	
					If study stops	If study continues
60	Intent-to-Treat	DVT1	Patient Profile for Deep Vein Thrombosis/Pulmonary Embolism	Non-ICH Listing Conditional output that will only be produced if participant have corresponding event	AAC	AAC
61	Intent-to-Treat	MI1	Patient Profile for Myocardial Infarction	Non-ICH Listing Conditional output that will only be produced if participant have corresponding event	AAC	AAC
62	Intent-to-Treat	PATE1	Patient Profile for Peripheral Arterial Thromboembolism	Non-ICH Listing Conditional output that will only be produced if participant have corresponding event	AAC	AAC
63	Intent-to-Treat	PUL1	Patient Profile for Pulmonary Hypertension	Non-ICH Listing Conditional output that will only be produced if participant have corresponding event	AAC	AAC

Listings						
No.	Population	IDSL / Example Shell	Title	Programming Notes	Deliverable	
					If study stops	If study continues
64	Intent-to-Treat	REV1	Patient Profile for Revascularisation	Non-ICH Listing Conditional output that will only be produced if participant have corresponding event	AAC	AAC
65	Intent-to-Treat	VAL1	Patient Profile for Valvulopathy	Non-ICH Listing Conditional output that will only be produced if participant have corresponding event	AAC	AAC
66	Intent-to-Treat	DD3	Subject Profile for Death	Non-ICH Listing Conditional output that will only be produced if participant have corresponding event	AAC	AAC

11.10. Appendix 10: Qualifying Uropathogen Algorithm

[figure not shown]
Qualifying Uropathogen Decision Tree: Single Uropathogen

[figure not shown]
*Pure culture: a culture containing the growth of a single strain of organism free from other pathogens or normal flora.

Qualifying Uropathogen Decision Tree: 2 Uropathogens

Note: Since *Enterococcus* spp., beta-hemolytic streptococci, *Gardnerella vaginalis* and *Aerococcus urinae* must be present in pure culture to be considered a uropathogen, the 2 or ≥ 3 uropathogens trees do not apply to these organisms.

[figure not shown]
Qualifying Uropathogen Decision Tree: ≥ 3 Uropathogens

Note: Since *Enterococcus* spp., beta-hemolytic streptococci, *Gardnerella vaginalis* and *Aerococcus urinae* must be present in pure culture to be considered a uropathogen, the 2 or ≥ 3 uropathogens trees do not apply to these organisms.

[figure not shown]
11.11. Appendix 11: Uropathogen Phenotype Algorithm

ESBL Decision Tree

[figure not shown]
Note: ESBL not determined for other Gram-negative organisms.

Methicillin* Decision Tree

*Cefoxitin is tested as a surrogate test for oxacillin to determine methicillin susceptibility/resistance. Methicillin-(oxacillin) resistant staphylococci are resistant to all currently available beta-lactams, cephalosporin and carbapenem antimicrobial agents, with the exception of ceftaroline.

Multi-drug Resistance (MDR) Decision Tree

*Cefoxitin is tested as a surrogate test for oxacillin to determine methicillin susceptibility/resistance. Methicillin-(oxacillin) resistant staphylococci are resistant to all currently available beta-lactams, cephalosporin and carbapenem antimicrobial agents, with the exception of ceftaroline.

Antimicrobial Resistant Phenotypes

CONFIDENTIAL

212390

Antimicrobial class	Antimicrobial	Drug relevant to Gram-negatives	Drug relevant to Gram-positives	Resistant phenotype to be reported if interpretation is resistant*
Penicillin	Ampicillin	X	X	AMP-R
	Mecillinam	X		MEC-R
	Penicillin		X	PEN-R
B-lactam combination	Amoxicillin/clavulanic acid	X		AUG2-R
	Ceftolozane/tazobactam	X		C/T-R
	Ceftazidime/avibactam	X		CZA-R
	Piperacillin/tazobactam	X		P/T4-R
Cephalosporin	Cefazolin	X		FAZ-R
	Ceftriaxone	X		AXO-R
	Cefadroxil	X		CFR-R
	Cefoxitin**		X	See methicillin resistance tree
Carbapenem	Meropenem	X		MERO-R
Aminoglycoside	Amikacin	X		AMI-R

CONFIDENTIAL

212390

	Gentamicin	X		GEN-R
Folate Pathway Antagonist	Trimethoprim-sulfamethoxazole	X	X	SXT-R
	Trimethoprim	X	X	TMP-R
	Sulfisoxazole	X	X	SFX-R
Fluoroquinolone	Ciprofloxacin	X	X	CIP-R
	Levofloxacin	X	X	LEV-R
Nitrofurantoin	Nitrofurantoin	X	X	NIT-R
Glycopeptide	Vancomycin		X	VAN-R
Fosfomycin	Fosfomycin	X	X	FOF-R
Nitroxoline	Nitroxoline	X	X	NOX-R

*resistant phenotype based on CLSI M100 interpretations with the exception of nitroxoline and cefadroxil which are based on EUCAST interpretations

**Surrogate test for oxacillin to determine methicillin susceptibility/resistance

R=resistant

11.12. Appendix 12: Uropathogen Genotype Algorithm

Gepotidacin Study 212390 – Genotype Analysis

Genotype Description	Details	When Performed	Example Reporting Values
Whole Genome Sequencing			
Screen for beta-lactamase genes	
 1. Beta-lactamase screening 2. Extended-spectrum beta-lactamases (ESBL) 3. Original-spectrum beta-lactamases 4. Plasmid-mediated AmpC beta-lactamases 5. Extended spectrum AmpC 6. carbapenemases 7. uncategorized spectrum beta-lactamase 8. Chromosomal AmpC 	
Enterobacterales isolates (except P. mirabilis) with MIC results of ≥ 2 $\mu\text{g/mL}$ for ceftriaxone and/or ceftazidime and/or cefotaxime, and/or aztreonam
 
P. mirabilis with MIC results of ≥ 2 $\mu\text{g/mL}$ for cefpodoxime and/or ceftazidime and/or cefotaxime
 
Enterobacterales isolates with MIC results of ≥ 2 $\mu\text{g/mL}$ for meropenem
	
 1. pos/neg 2. CTX-M-15* 3. TEM-1* 4. CMY-2* 5. EC-6* 6. KPC-3* 7. SHV-35* 8. PDC-30*
Screen for plasmid-mediated fluoroquinolone resistance (FQ-R) genes	
 • Genes from the gnr family 
 1. FQ screening 2. Aminoglycosides 	
 • Isolates resistant to FQs (levofloxacin or ciprofloxacin) • E. coli isolates with gepotidacin MICs ≥ 8 mcg/mL 	
 1. pos/neg 2. aac(6')-Ib-cr, gnrB, oqxA*
Screen for gene mutations of the	
 • Mutations in the FQ binding region GyrA 	
 • Isolates resistant to FQs (levofloxacin or ciprofloxacin) 	
“wildtype” or S81F, delS81F, S81Fins

CONFIDENTIAL

212390

Genotype Description	Details	When Performed	Example Reporting Values
quinolone (FQ) resistant determining region (QRDR)	
 • Mutations in the FQ binding region GyrB 	
 • E. coli isolates with gepotidacin MICs ≥ 8 mcg/mL 	“wildtype” or G425E, delG425, G425ins
	
 • Mutations in the FQ binding region grlA 		“wildtype” or S80F, delS80, S80ins
	
 • Mutations in the FQ binding region grlB 		“wildtype” or D432N, delD432, D432ins
	
 • Mutations in the FQ binding region parC 		“wildtype” or S79F, dels79, S79ins
	
 • Mutations in the FQ binding region parE 		“wildtype” or V90A, delV90, V90ins
MLST (multi-locus sequence typing)	
 • 7 housekeeping genes sequenced 	
Enterobacterales isolates (except P. mirabilis) with MIC results of ≥ 2 $\mu\text{g/mL}$ for ceftriaxone and/or ceftazidime and/or cefotaxime, and/or aztreonam
 
P. mirabilis with MIC results of ≥ 2 $\mu\text{g/mL}$ for cefpodoxime and/or ceftazidime and/or cefotaxime
 
Enterobacterales isolates with MIC results of ≥ 2 $\mu\text{g/mL}$ for meropenem
 
E. coli isolates with gepotidacin MICs ≥ 8 mcg/mL
	ST131*

[figure not shown]
Genotype Description	Details	When Performed	Example Reporting Values
O:H serotyping	
 Typing of the lipopolysaccharide (LPS) (O antigen) and the flagellar (H) antigens of E. coli 	
E. coli isolates with MIC results of ≥ 2 $\mu\text{g/mL}$ for ceftriaxone and/or ceftazidime and/or cefotaxime, and/or aztreonam
 
E. coli isolates with MIC results of ≥ 2 $\mu\text{g/mL}$ for meropenem
	O157:H7*
fimH typing	
 fimH is a bacterial cell surface component that facilitates adhesion to other cells 	E. coli isolates designated as MLST131	fimH27 *
Clonal assessment of microbiological failures (by MLST or PFGE)	
 See MLST description above PFGE (pulse field gel electrophoresis): assessment of isolate genetic relatedness (performed only if MLST typing is unavailable) 
 PFGE_type PFGE_similarity PFGE_interpretation 	
 all isolates from patients who were a microbiological failure 	
 MLST: same as above PFGE: allowed values: 
 alpha/numeric (eg, "A1") allowed values: any percentage (eg, 99.5%) allowed values: baseline, identical to baseline, related to baseline, or unrelated to baseline
Expression Analysis			
Expression of AmpC (chromosomally encoded)	
 gene expression from clinical isolates will be compared to expression from reference strains 
 AmpC expression value AmpC expression interpretation 	
 For the following isolates in which no beta-lactamases were detected Enterobacterales isolates (except P. mirabilis) with MIC 	
 numeric RQ value (eg 0.845766776)* allowed values: 
 similar to baseline (0 to <5)

Genotype Description	Details	When Performed	Example Reporting Values
		results of ≥ 2 $\mu\text{g/mL}$ for ceftriaxone and/or ceftazidime and/or cefotaxime, and/or aztreonam 
 • P. mirabilis with MIC results of ≥ 2 $\mu\text{g/mL}$ for cefpodoxime and/or ceftazidime and/or cefotaxime • Enterobacterales isolates with MIC results of ≥ 2 $\mu\text{g/mL}$ for meropenem 	b. moderate expression (5 to <10) c. overexpression (≥ 10)
Expression of AcrAB (efflux pump)	
 • same as for AmpC 	
 • FQ-resistant E. coli isolates for which no QRDR or plasmid mutations were detected • E. coli isolates with gepotidacin MICs ≥ 8 mcg/mL 	
 • same as for AmpC

*Numerous results are possible for these test codes.

Example outputs from published studies:

Microbiological Eradication at TOC by β -Lactamase Genotype of Uropathogens
High rates of eradication were achieved across pathogens with β -lactamase genes

^aIncludes *bla*_{CTX-M-15}-like.
^bIncludes *bla*_{OXA-1/OXA-30}-like.
^cIncludes *bla*_{TEM-1}-like.
^dIncludes *bla*_{SHV-1}-like.
^eIncludes all variants of *bla*_{ACT}, *bla*_{CMY} and *bla*_{DHA}.

Table 1. Per-Pathogen Microbiological Eradication at TOC^a by Resistance Phenotype and Resistance Mechanism (Extended mMITT Population)			
Pathogen	PLZ (N = 202) n/N1 (%)	MEM (N = 205) n/N1 (%)	Difference PLZ Minus MEM (95% CI)
Overall	191/215 (88.8)	164/222 (73.9)	15.0 (7.4 to 22.4)
Enterobacteriaceae	189/213 (88.7)	161/217 (74.2)	14.5 (6.9 to 22.0)
AG-NS phenotype ^b	46/60 (76.7)	37/58 (63.8)	12.9 (-4.8 to 29.6)
ESBL phenotype ^c	47/59 (79.7)	47/67 (70.1)	9.5 (-6.9 to 25.0)
AME-gene positive ^d	51/67 (76.1)	49/75 (65.3)	10.8 (-5.3 to 25.9)
aac(6')Ib-cr	29/38 (76.3)	29/41 (70.7)	5.6 (-15.5 to 25.8)
aac(3)-IIa	18/25 (72.0)	21/31 (67.7)	4.3 (-22.0 to 28.7)
β-Lactamase-gene positive ^d	62/80 (77.5)	53/81 (65.4)	12.1 (-2.8 to 26.2)
bla _{CTX-M-15}	39/48 (81.3)	36/50 (72.0)	9.3 (-9.0 to 26.7)
bla _{OXA-1/OXA-30}	31/42 (73.8)	27/40 (67.5)	6.3 (-14.7 to 26.8)
^a Microbiological eradication defined as a reduction in baseline pathogen from $\geq 10^5$ CFU to $< 10^4$ CFU in urine culture. ^b AG-NS defined as nonsusceptible interpretation (intermediate or resistant) to any of amikacin, gentamicin, or tobramycin based on central laboratory MIC testing and Clinical and Laboratory Standards Institute 2016 breakpoints. ^c ESBL phenotype defined as MIC ≥ 2 $\mu\text{g}/\text{mL}$ to any of ceftazidime, aztreonam, or ceftriaxone based on central laboratory testing. ^d All isolates with AG-NS and ESBL phenotypes were sequenced for both AME and ESBL genes. N, number of patients in the specified population; N1, number of uropathogens in the specified category at baseline; n, number of uropathogens eradicated in the specified category. CFU, colony forming units; CI, confidence interval; ESBL, extended-spectrum β-lactamase; MIC, minimum inhibitory concentration; MIC _{50/90} , minimum inhibitory concentration required to inhibit the growth of 50%/90% of organisms; mMITT, microbiological modified intent-to-treat; NS, nonsusceptible; TOC, test of cure.			

Note: Uropathogen genotypic subcategories may be reported individually (e.g. *bla*_{CTX-M-15}) or grouped together (e.g. ESBL-gene positive) for reporting, dependent on numbers recovered and epidemiological significance. See examples above. The potential individual and group categories will be monitored in stream during the study and provided by the GSK microbiology team.

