5.4.2. Examination of Subgroups

Subgroup analyses will be performed using the following categories for efficacy analysis; treatment group differences will be displayed for subgroups with ≥10 participants across both treatment groups. For the subgroup analyses related to age category and acute cystitis, in the event that participants are mis-stratified, the actual stratification will be created using actual age and recurrent status collected from eCRF. If the number of participants is small within a subgroup, then the subgroup categories may be refined prior to unblinding the trial.

- Age category (<18, ≥18 to 50, >50) (only for therapeutic, clinical and (participant-level) microbiological response analyses)
- Acute cystitis recurrence (nonrecurrent infection, recurrent infection) (nonrecurrent infection or recurrent infection, defined as a confirmed infection)

- with at least 1 episode within the past 3 months, at least 2 episodes within the past 6 months, or at least 3 episodes within the past 12 months before study entry) (only for therapeutic, clinical and (participant-level) microbiological response analyses)
- (Unpooled) Stratification combinations as above for age and acute cystitis recurrence (only for therapeutic, clinical and (participant-level) microbiological response analyses)
 - Qualifying uropathogen species/group isolated at Baseline (including phenotypic and genotypic subcategories), which is defined in Section 7.3.2. (only for therapeutic, clinical and (uropathogen-level) microbiological response analyses)
 - Number of Qualified Uropathogens at Baseline (only 1 qualifying uropathogen, two qualified uropathogens, one qualified plus additional any number of non-qualified uropathogens, only for therapeutic response)
 - Region (only for therapeutic, clinical and (participant-level) microbiological response analyses):
 - Americas: United States
 - Europe: Bulgaria and Poland
 - Asia-Pacific: Australia, India and South Korea
 - Others
 - Race (only for therapeutic, clinical and (participant-level) microbiological response analyses)
 - Ethnicity (only for therapeutic, clinical and (participant-level) microbiological response analyses)
 - Menopausal status: Post-menopausal vs. Non post-menopausal (only for therapeutic, clinical and (participant-level) microbiological response analyses)
 - Baseline symptom total scores (2-5, 6-8, 9-12) (only for therapeutic, clinical and (participant-level) microbiological response analyses)

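### Sequence typing in SAP Appendix 12 depends on outcome, so any sequence-type or fimH response subgroup built from all typed isolates would understate success

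*SAP*

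**What the plan says.** SAP Section 11.12 (Appendix 12) sets out two routes to a sequence type.

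- **By susceptibility.** Enterobacterales other than *P. mirabilis* are typed at an MIC of at least 2 µg/mL "for ceftriaxone and/or ceftazidime and/or cefotaxime, and/or aztreonam". Similar rules cover *P. mirabilis* and meropenem. *E. coli* "isolates with gepotidacin MICs ≥ 8 mcg/mL" are typed as well.
- **By outcome.** A separate row for the clonal assessment of failures types "all isolates from patients who were a microbiological failure", by MLST or, if that is unavailable, by PFGE. It carries no MIC condition, and successes have no matching rule. Its reporting column refers back to the MLST row, so both routes yield the same kind of value.

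fimH typing then applies to *E. coli* "isolates designated as MLST131", whichever route produced the designation.

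Microbiological failure is broad. Under SAP Table 6 it includes a missing TOC culture and receipt of other systemic antimicrobials before TOC.

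On use, SAP 5.4.2 lists as an efficacy subgroup "Qualifying uropathogen species/group isolated at Baseline (including phenotypic and genotypic subcategories), which is defined in Section 7.3.2". Table 12 repeats this, and Figures 2.5 to 2.7 plot it, for example "Forest Plot for Therapeutic Success Rate by Qualifying Baseline Uropathogen and Uropathogen Phenotypic and Genotypic Subcategories". Section 7.3.2 is redacted in the public SAP. SAP 11.4.4 describes genotype results reaching the analysis database in one stream and a sponsor review that flags the subcategories to report. Neither step, as described, records why an isolate was typed. There is also a dedicated output for typed failures, Listing 26: "Listing of Sequence Typing and Phenotypic Subcategories for Qualifying Uropathogens from Microbiological Failures".

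**The concern.** Take a baseline isolate of some sequence type that meets no MIC trigger. If the participant is a microbiological failure, the isolate is typed and can enter that type's subgroup. If she is a success, it is never typed and cannot. Membership of the subgroup would then depend on the endpoint analysed within it, and failures would be over-represented. Some would be failures only because a culture was missing or another antimicrobial was given.

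At stake is the descriptive reading of response by clone. ST131 is the natural example: Appendix 12 gives it as its sample MLST value, and Protocol 2.2 cites the clone as one reason for the resistance threat. A low success rate for such a clone could be read as a property of the organism when it came from the typing rule.

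The rule can also influence which categories appear. Appendix 12 makes reporting depend partly on numbers recovered, and 5.4.2 displays treatment differences for subgroups of at least 10 participants. Failure-triggered isolates add to those counts.

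**Working it through.** The plan states no figure on this point, so there is none to reproduce.

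**Inputs**
- s, the true microbiological success rate within a sequence type. The documents give none. I use 76%, the therapeutic rate in Protocol 9.2.1, as a stand-in, and show 66% to 90%.
- q, the share of the type's baseline isolates that meet an MIC trigger. This is not in the documents. I show 0.25 to 1 and take q as independent of outcome and equal in both arms. Strictly, only the share among successes enters the formula, because every failure is typed anyway.

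**Microbiological response.** Typed successes are q·s and typed failures are 1 − s, so

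reported rate = q·s / (q·s + 1 − s).

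With 100 isolates, s = 76% and q = 0.5, there are 76 × 0.5 = 38 typed successes and 24 typed failures: 38/62 = 61.3%.

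| True s | q = 0.25 | q = 0.50 | q = 0.75 | q = 1 |
|---|---|---|---|---|
| 66% | 32.7% | 49.3% | 59.3% | 66% |
| 76% | 44.2% | 61.3% | 70.4% | 76% |
| 80% | 50.0% | 66.7% | 75.0% | 80% |
| 90% | 69.2% | 81.8% | 87.1% | 90% |

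The reported rate equals the true rate only at q = 1.

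**Between-arm difference**, control at 76%, same q in both arms:

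| True difference | q = 0.25 | q = 0.50 | q = 0.75 |
|---|---|---|---|
| 0 | 0 | 0 | 0 |
| −10 points | −11.5 | −12.0 | −11.1 |
| +10 points | +16.4 | +14.1 | +11.8 |

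**Which visit defines failure.** Appendix 12 does not say. If failure at Follow-up also triggers typing, a share r of TOC successes is typed as well. Typed TOC successes become s·(r + (1 − r)·q). At s = 76% and q = 0.5:
- r = 0.10: 0.76 × 0.55 = 0.418, and 0.418/(0.418 + 0.24) = 63.5%.
- r = 0.20: 0.76 × 0.60 = 0.456, and 0.456/(0.456 + 0.24) = 65.5%.

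The TOC understatement shrinks but remains.

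**Therapeutic response.** Every microbiological failure is a therapeutic failure. With true therapeutic success t, the reported rate is q·t / (q·s + 1 − s). The denominator exceeds q by (1 − s)(1 − q), so the reported rate is below t whenever q < 1 and s < 1. The size needs t and s separately, and the documents do not give both, so the tables above do not apply to it. They do not apply to clinical response either, where the effect depends on how clinical and microbiological outcomes go together.

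**Scope.** The Appendix 12 rows for beta-lactamase genes, fluoroquinolone-resistance genes, QRDR mutations, O:H serotype and gene expression have no failure trigger. Only MLST and fimH categories are exposed.

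**The case against.** The strongest reply is that the step from typing to biased results cannot be seen. The genotypic subcategories are defined in Section 7.3.2, which is redacted, and redacted text cannot be treated as absent from the plan. No visible passage names ST131 or fimH as a tabulated response subgroup. Appendix 12 leaves the choice to the sponsor's microbiology team, and its examples are resistance phenotypes and genes, which are not exposed. The failure rule is labelled as a clonal assessment, its PFGE results express relatedness to baseline, and Listing 26 is a natural home for it. All of this stands. A reader might infer that the plan's ST131 or fimH success rates are biased. The documents do not support that; they support a conditional statement.

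The numerical objections also stand. q is not in the documents. Because one trigger is a gepotidacin MIC, q may not be independent of outcome or equal across arms, least of all in the gepotidacin arm. Consequence is limited too: under SAP 5.5 the efficacy analyses other than the primary are descriptive.

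The mechanism itself is not answered. The two routes give indistinguishable values, and no visible text separates them before the subgroup analyses. Listing 26 shows one use of the failure-triggered results but does not exclude another. Finalising category lists before unblinding does not help, because the selection is on outcome rather than on treatment.

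**Conclusion.** The point holds in conditional form. Sequence typing and the fimH typing that follows it depend on outcome. If sequence-type or fimH categories are used as baseline response subgroups and include all typed isolates, microbiological success is understated unless every isolate of that type met an MIC trigger. As an illustration, a true 76% would show as about 61% at q = 0.5, and as 70% to 44% for q from 0.75 down to 0.25. This rests on an assumed q, independent of outcome, and on 76% as a stand-in. Therapeutic rates are also pulled down, by an amount the formula does not give.

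The main distortion is in the within-arm rates. A reader might go further and infer a threat to the treatment comparison. With equal q a zero difference stays zero, although non-zero differences are distorted. The primary analysis is not touched, and neither are the resistance-gene, QRDR, O:H and expression subgroups.

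**What to change.** State in Appendix 12 and SAP 5.4.2 that any sequence-type or fimH subgroup used in a response analysis (Table 12, Figures 2.5 to 2.7) contains only baseline isolates that met one of the MIC-based triggers, and label it so in the output. Appendix 12 does not confine the MIC triggers to baseline isolates, so the baseline condition needs to be explicit. Add a flag for the typing route. Use MLST, PFGE or fimH results obtained only because of failure solely for the clonal assessment and Listing 26. State which visit defines microbiological failure for typing. If Section 7.3.2 already contains this restriction, a cross-reference is enough.

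The cost is a short text change and one derivation flag, with no new testing. The subgroups become smaller, and they describe MIC-triggered isolates of the type rather than all isolates of that type. If q is related to outcome, those two success rates differ, which is why the label matters.
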